18. TRANSLATIONAL STUDIES

18.1. Early side effects translational sub-study

Patients included in the early side effects sub-study will be asked if they are willing to donate blood samples for the following associated translational study. Participation will be optional and subject to patients' written informed consent.

Rationale: Radiotherapy can have immunomodulatory effects on tumour and surrounding normal tissues(56). Studies have shown that, in normal tissues exposed to radiotherapy, acute immune cell changes and release of pro-inflammatory cytokines can ultimately lead to chronic inflammation and radiotherapy-induced toxicity (e.g. pneumonitis and fatigue), which limits quality of life(56).

Radiation-induced lymphopenia (RIL) has been described in several solid tumours, with severe lymphopenia linked to poorer prognosis(57, 58). A study comparing 50Gy/25#/5 weeks versus 43.5Gy/15#/3 weeks of radiotherapy in breast cancer patients found that the risk of RIL was lower with the 3-week regimen in which total dose is lower(59). In addition, a lower ratio of nadir peripheral lymphocyte count during radiation to peripheral lymphocyte count before radiation predicted poorer prognosis in patients with breast cancer(59). Field size and irradiated volume are also known to influence radiation-induced immune effects(57, 60).

The FAST-Forward Boost early side effects study provides a unique opportunity to study the systemic immune consequences of different radiotherapy fractionation regimens and treatment volumes and to explore the association with radiotherapy-induced side effects.

Objectives: The primary objective is to assess differences in radiation-induced immune-inflammatory changes in blood for patients in the Control Group (3-week schedule) compared with Test Groups (1-week schedule). Secondary objectives will explore differences in these changes according to treated volume, and consider associations with the incidence and severity of acute toxicity endpoints.

Endpoints: The primary endpoint is the incidence of CTCAE grade ≥ 2 lymphopenia (based on central assessment of blood samples at both follow-up time points during the sub-study). Secondary endpoints include: ratio of nadir lymphocyte count to pre-treatment lymphocyte count, and clinician-reported and patient-reported acute toxicity endpoints (e.g. pneumonitis, skin toxicity, fatigue) as assessed in the trial.

Design and sample analysis: Blood will be collected at 3 time points, aligned with clinician assessment of acute toxicity in the early side effects sub-study: baseline (prior to start of radiotherapy); on the final day of radiotherapy; and 2 weeks following completion of radiotherapy. 2X10ml EDTA tubes will be collected at each timepoint for immediate processing into component parts. Whole blood flow cytometry analysis will be conducted using bespoke panel/s to capture the wider immune cell repertoire. An initial pilot assessment in 40-50 patients (120-150 samples) will assess technical feasibility of the approach.

Statistical considerations: With the 3-week (Control) radiotherapy schedule, 25% of patients are expected to have grade ≥ 2 lymphopenia(59). We hypothesize that this will be approximately halved with the 1-week schedule (to 12%, a 13% reduction). In order to have 80% power to detect this difference with a one-sided alpha=0.05 requires 240 patients (80 Control Group, 160 Test Groups). Since participants in this translational sub-study will also need to be participating in the early side effects sub-study, recruitment to these studies will run in parallel and the final sample size for the translational work will be determined by the recruitment period remaining for the early side effects sub-study at the time of implementation. The power calculation is indicative of what we might expect to achieve but it is acknowledged that a smaller sample size is possible. Furthermore, smaller difference between groups could be important and may not be detectable within this study. As such, the analysis is seen as exploratory and will inform future work in this area.

Incidence of grade ≥ 2 lymphopenia (based on highest grade observed during/post-treatment) will be compared between the Control and Test Groups using a chi-squared test. The ratio of nadir lymphocyte count to pre-treatment lymphocyte count will be compared using t-test or non-parametric equivalent. The two Test Groups will be combined since no difference is expected. Other analyses will be largely descriptive. Incidence of lymphopenia and ratio of nadir to pre-treatment lymphocyte count will be considered according to treatment volume, and will also be cross-tabulated with acute toxicity endpoints.

Data from the pilot assessment will be reviewed by the IDMC as part of their routine trial monitoring. Final statistical analysis will be conducted when all sample collection and analysis is complete. Full details of statistical analysis will be specified in a Statistical Analysis Plan.

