8.12. Treatment Timelines

Radiotherapy should commence as soon as possible and ideally within 4 weeks of randomisation. It is advised that radiotherapy starts within 8 weeks of surgery and/or last dose of chemotherapy when possible. Timelines from systemic therapy to start of radiotherapy should otherwise be observed as per standard of care.

(please see section 8.15 for advice about timing with systemic therapy).

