8.15. Concomitant Therapy

TDM-1 can be given concomitantly with radiotherapy but, in the test groups, it is recommended that TDM-1 should not be given within 4 days prior to (or after) a fraction of radiotherapy. For the control group, it is accepted that one TDM-1 dose will be given on the same day as a radiotherapy fraction.

Where CDK4/6 inhibitors are recommended, these should ideally be given no earlier than 7 days following completion of radiotherapy. If CDK4/6 inhibitors have been started prior to trial randomisation, they should be stopped at least 7 days prior to the first radiotherapy fraction and can be restarted 7 days after the final fraction.

Immunotherapy can be started before radiotherapy, but doses of immunotherapy should not be given within 7 days prior to the first fraction of radiotherapy or within 7 days of the last fraction of radiotherapy.

Concomitant endocrine therapy, bisphosphonate, denosumab, trastuzumab and pertuzumab *are* permitted.

Other chemotherapy agents (including adjuvant anthracyclines, taxanes and capecitabine) and other biological/targeted therapies (e.g. PARP inhibitors) are not permitted to be delivered concomitantly with radiotherapy. Standard departmental protocols of timing of these agents in relation to radiotherapy should be followed. Contact the ICR-CTSU if any clarification around systemic therapies is required.

It is recommended that radio-sensitising agents such as methotrexate are discontinued for at least one week prior to and after completion of radiotherapy. Otherwise, all medication considered necessary for the patient's welfare, and which is not expected to interfere with the evaluation of the treatment may be given at the discretion of the investigator. All concomitant medications (including start/stop dates, dose frequency, route of administration and indication) must be recorded in the patient's notes.

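### The primary lymphopenia endpoint of the early side effects translational sub-study counts patients who were already at grade 2 or worse before radiotherapy, which dilutes the comparison of schedules

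*Protocol*

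**What the plan says.** All of this is in the protocol.

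- **Objective (section 18.1).** "The primary objective is to assess differences in radiation-induced immune-inflammatory changes in blood" between the Control Group and the Test Groups.
- **Primary endpoint (section 18.1).** Incidence of CTCAE grade 2 or worse lymphopenia, "based on central assessment of blood samples at both follow-up time points during the sub-study".
- **Primary analysis (section 18.1).** The incidence is "based on highest grade observed during/post-treatment) will be compared between the Control and Test Groups using a chi-squared test". The two test groups are pooled, and no covariate is named.
- **Use of the baseline count (section 18.1).** The ratio of nadir to pre-treatment lymphocyte count is a named secondary endpoint with its own between-group test. It is also to be looked at by treatment volume and cross-tabulated with acute toxicity.
- **Sample size (section 18.1).** "With the 3-week (Control) radiotherapy schedule, 25% of patients are expected to have grade" 2 or worse lymphopenia, and this is expected to be "approximately halved with the 1-week schedule (to 12%, a 13% reduction"). The requirement is stated as "80% power to detect this difference with a one-sided alpha=0.05 requires 240 patients (80 Control Group, 160 Test Groups").
- **Samples (sections 8.4 and 8.6).** For patients in this sub-study the first sample must precede radiotherapy. The two follow-up samples fall at the end of weeks 1 and 3 from the start of radiotherapy in the test groups, and at the end of weeks 3 and 5 in control.

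**The concern.** The objective is about change caused by radiation, while the primary endpoint is an absolute state after radiotherapy. The two differ for anyone who enters with a low count. Such a patient is scored as an event in either arm, so the endpoint mixes the quantity of interest with a background that fractionation cannot alter.

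Prior systemic treatment is foreseen in this population. Section 8.12 advises that "radiotherapy starts within 8 weeks of surgery and/or last dose of chemotherapy when possible". Section 8.15 says of CDK4/6 inhibitors begun before randomisation that "they should be stopped at least 7 days prior to the first radiotherapy fraction and can be restarted 7 days after the final fraction". A low pre-treatment count in some patients is therefore a possibility the endpoint should handle, whatever its cause.

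What is at stake is a blurred contrast in a small comparison that section 18.1 says may end up smaller still. A weak result could be read as no difference between schedules when part of the explanation is background lymphopenia that the sub-study had measured.

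**Working it through.** **Inputs from section 18.1.** Control rate p1 = 0.25, test rate p2 = 0.12, n1 = 80, n2 = 160, one-sided alpha 0.05 (z = 1.645).

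**Input not in the documents.** The share b already at grade 2 or worse in the pre-treatment sample. Values of 5%, 10% and 20% are assumed.

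**Step 1: reproduce the plan's figure.** Two-proportion test, pooled variance under the null, no continuity correction:

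power = Φ[(p1 − p2 − 1.645 × SE0) / SE1], where SE0 = √[p̄(1 − p̄)(1/80 + 1/160)], p̄ is the pooled rate, and SE1 = √[p1(1 − p1)/80 + p2(1 − p2)/160].

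- p̄ = (0.25 + 2 × 0.12)/3 = 0.1633
- SE0 = 0.0506, SE1 = 0.0548
- power = Φ[(0.13 − 0.0833)/0.0548] = Φ(0.853) = 80.3%

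The sample size formula on the same basis returns 80 + 160 = 240, so the stated figure is reproduced.

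**Step 2: let prevalent cases count as events.** Read 25% and 12% as rates among patients not lymphopenic at baseline. The observed rates become b + (1 − b) × 0.25 and b + (1 − b) × 0.12. For b = 10%:

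- control 0.10 + 0.90 × 0.25 = 0.325; test 0.10 + 0.90 × 0.12 = 0.208; difference 0.117
- SE0 = 0.0591, SE1 = 0.0614
- power = Φ[(0.117 − 0.0971)/0.0614] = Φ(0.323) = 62.7%

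**Step 3: count only incident cases among the same 240.** The rates return to 25% and 12%, and the group sizes shrink to 80(1 − b) and 160(1 − b). For b = 10% this is 72 and 144, with power 76.8%.

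| Assumed b | Observed rates, control / test | Power, endpoint as written | Power, incident cases only |
|---|---|---|---|
| 0 | 25.0% / 12.0% | 80.3% | 80.3% |
| 5% | 28.8% / 16.4% | 71.1% | 78.6% |
| 10% | 32.5% / 20.8% | 62.7% | 76.8% |
| 20% | 40.0% / 29.6% | 48.8% | 72.7% |

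The last column drops baseline cases altogether and takes no credit for covariate adjustment. It approximates the event definition proposed below and is not an exact power for it.

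**Step 4: is this bias?** With the same b in both arms and the same radiation-induced rate (20% assumed), the one-sided error rate was simulated with 200,000 replicates per setting: 0.052 at b = 0, 0.051 at b = 10% and 0.051 at b = 20%. A common background does not create a false difference.

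**The case against.** **The baseline count is used.** True. The nadir/pre-treatment ratio is a tested secondary endpoint, so it would be wrong to say that the sub-study ignores the pre-treatment sample. The point is limited to the primary endpoint and its test.

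**The detail belongs in the analysis plan.** Section 18.1 defers full analysis detail to a statistical analysis plan, which is not shown. Further covariates and sensitivity analyses can fairly wait for it. But the event definition and the test are stated in the protocol, and a plan that followed them would carry the mismatch forward.

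**The 25% may already include baseline cases.** The wording describes patients expected to have lymphopenia, which can be read as an overall rate. Suppose 25% includes b and only the remainder falls in the ratio 12/25 = 0.48. With b = 5% the test rate is 0.05 + 0.20 × 0.48 = 14.6% and power is 62.2%, or 71.4% with baseline cases excluded. With b = 10% the test rate is 0.10 + 0.15 × 0.48 = 17.2%, with 41.8% and 60.2%. This reading changes the size of the loss but not its direction.

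**A reader might infer that the comparison is biased by permitted drugs.** The documents do not support that. They do not say that any of these drugs lowers lymphocytes, and they give neither a prevalence nor the share of patients treated. The CDK4/6 inhibitor and immunotherapy windows after radiotherapy run from the final fraction alike in all groups. The TDM-1 rule in section 8.15 differs by arm, but it recommends a 4-day gap in the test groups and accepts a dose on a fraction day in control, so no single direction follows. What does differ is when blood is drawn: weeks 1 and 3 against weeks 3 and 5. Time since earlier systemic treatment therefore differs by arm. That is a limitation, and its size cannot be worked out from the protocol.

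**The sub-study is exploratory.** It is optional, its power figure is called indicative, and a smaller sample is acknowledged. This stands and keeps the point minor.

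**Conclusion.** The point holds in a limited form and is minor. The primary endpoint and its unadjusted test do not match an objective about radiation-induced change, because patients already at grade 2 or worse before radiotherapy count as events. The consequence is dilution. With 25% and 12% read as new-case rates, power falls from 80% to about 71%, 63% or 49% for an assumed baseline share of 5%, 10% or 20%; counting incident cases only restores it to about 79%, 77% or 73%. These sizes rest wholly on the assumed share, and if almost no one is lymphopenic at baseline the loss is negligible. The stated 240 patients are correct for the stated inputs. The protocol does not support a finding of systematic bias.

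**What to change.** In section 18.1, and then in the sub-study's analysis plan:

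1. Define the primary event as new or worsened grade 2 or worse lymphopenia relative to the pre-treatment sample. A patient already at grade 2 or worse counts only if the grade rises.
2. Replace the unadjusted chi-squared test with a logistic regression comparing Control with the combined Test Groups, adjusted for pre-treatment lymphocyte count.
3. State whether the 25% and 12% are meant as new-case rates.
4. Record as a limitation that follow-up samples fall at weeks 1 and 3 in the test groups and weeks 3 and 5 in control. Time since earlier systemic treatment therefore differs by arm, and baseline adjustment deals with this only in part.

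Two tempting additions should be left out. Excluding patients by drug exposure after radiotherapy would condition on something that happens after randomisation. Using only the final-fraction sample would compare week 1 in the test groups with week 3 in control and so keep the timing difference.

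The cost is a change of wording. The pre-treatment sample is already required before radiotherapy for these patients, and no extra samples or patients are needed.

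### Adding the pre-treatment lymphocyte count as a covariate would usually sharpen the planned nadir-to-baseline ratio comparison at no cost; the unadjusted test is valid but can be inefficient

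*Protocol*

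**What the plan says.** Protocol section 18.1 sets out a translational sub-study with blood taken at three points: "baseline (prior to start of radiotherapy); on the final day of radiotherapy; and 2 weeks following completion of radiotherapy". Its primary endpoint is binary, the incidence of grade 2 or worse lymphopenia, and the sample size of 240 (80 Control, 160 Test) is built on it. The continuous endpoint is secondary: "Secondary endpoints include: ratio of nadir lymphocyte count to pre-treatment lymphocyte count".

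The method for that endpoint is named: "The ratio of nadir lymphocyte count to pre-treatment lymphocyte count will be compared using t-test or non-parametric equivalent". The test arms are pooled for it: "The two Test Groups will be combined since no difference is expected". Remaining analyses are described as largely descriptive, so this is the only continuous between-group test that the section names.

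On precision, the section says of the 240 that "it is acknowledged that a smaller sample size is possible". It adds that smaller differences might matter and go undetected, calls the analysis exploratory, and leaves full details to a statistical analysis plan.

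**The concern.** The sub-study's primary objective is to compare immune changes between the 3-week and 1-week schedules. A continuous count carries more information about that than a grade threshold, so the ratio comparison is where a modest difference would most likely show.

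On the log scale the ratio is log nadir minus log pre-treatment count, which is a change score. It fixes the coefficient of the pre-treatment count at 1 whatever the data say. If the true slope is below 1, subtracting the whole baseline puts part of its variation into the outcome; if it is above 1, too little is removed. ANCOVA estimates the slope and, apart from one degree of freedom, is never less precise. Both values are already measured in each patient who contributes a ratio, so no extra sample is needed.

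At stake is the width of the confidence interval on a secondary endpoint, in a sub-study whose own text expects limited precision.

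**Working it through.** **The plan's own figure first.** The 240 belongs to the binary endpoint: 25% against 12%, 80% power, one-sided 0.05, allocation 1:2.

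- Pooled proportion: (0.25 + 2 × 0.12)/3 = 0.1633.
- Null term: 1.645 × √(0.1633 × 0.8367 × 1.5) = 0.745.
- Alternative term: 0.842 × √(0.1875 + 0.1056/2) = 0.413.
- Control patients: (0.745 + 0.413)²/0.13² = 79.3, rounded up to 80. With 160 test patients the total is 240, and power is 80.3%.

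The figure reproduces and is not in dispute. No size, SD or power is stated for the ratio endpoint.

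**Inputs for the ratio endpoint.** From section 18.1: 80 against 160 patients, pooled test arms, one-sided 0.05. Assumed, because the protocol gives no value: the correlation ρ between log pre-treatment and log nadir count, the SD ratio k = SD(log baseline)/SD(log nadir), and, for power only, a log SD of 0.40 and a group effect of 0.12 on the log scale.

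**Variance factor.** Taking SD(log nadir) as 1:

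- Log ratio, unadjusted: 1 + k² − 2ρk.
- ANCOVA residual: 1 − ρ².
- ANCOVA relative to log ratio: (1 − ρ²)/(1 + k² − 2ρk).

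The true slope of log nadir on log baseline is ρ/k. When k = ρ the slope is 1, the factor is 1, and nothing is gained. When k = 1 the factor simplifies to (1 + ρ)/2.

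| ρ | k = 1 | k = 0.8 | k = 1.2 |
|---|---|---|---|
| 0.3 | 0.65 | 0.91/1.16 = 0.784 | 0.91/1.72 = 0.529 |
| 0.5 | 0.75 | 0.75/0.84 = 0.893 | 0.75/1.24 = 0.605 |
| 0.7 | 0.85 | 0.51/0.52 = 0.981 | 0.51/0.76 = 0.671 |
| 0.8 | 0.90 | 0.36/0.36 = 1.000 | 0.36/0.52 = 0.692 |

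With k = 1 the saving is 35%, 25%, 15% and 10%, so 240 patients act like 369, 320, 282 and 267. With k = 0.8 it is about 22%, 11%, 2% and 0% (306, 269, 245 and 240). With k = 1.2 it is 31% to 47%.

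**Power at the sub-study's one-sided 0.05, k = 1.** The standard error is the outcome SD times √(1/80 + 1/160) = 0.137. At ρ = 0.5, for example:

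- Log ratio: SD 0.40 × √(2 × 0.5) = 0.40, SE 0.0548, 0.12/0.0548 = 2.19, and 2.19 − 1.645 = 0.55, which gives 71%.
- ANCOVA: SD 0.40 × √0.75 = 0.346, SE 0.0474, 0.12/0.0474 = 2.53, and 2.53 − 1.645 = 0.89, which gives 81%.

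| ρ | Log ratio | ANCOVA |
|---|---|---|
| 0.3 | 58% | 74% |
| 0.5 | 71% | 81% |
| 0.7 | 88% | 92% |
| 0.8 | 97% | 98% |

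**Does the non-parametric option help?** In a simulation (2,500 runs per setting, 80 against 160, lognormal counts with a 40% coefficient of variation at both times, log effect 0.13, one-sided 0.05), power at ρ = 0.5 was 77% for the raw-ratio t-test, 77% for the rank test, 79% for the log-ratio t-test and 88% for ANCOVA. With coefficients of variation of 35% at baseline and 45% at nadir, the four figures were 76%, 77%, 78% and 83%. The rank test did not recover the loss, and ANCOVA was not worse in any setting tried.

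**Keeping the endpoint.** If log nadir = a + τ·group + b·log baseline, then log(nadir/baseline) = a + τ·group + (b − 1)·log baseline. The group effect τ is identical, so the ratio can stay as the outcome.

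**The case against.** The case against is substantial, and much of it stands.

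- *The planned test is not an error.* A reader might infer that a chance baseline difference between 80 and 160 patients biases the ratio comparison. It does not: randomisation makes the unadjusted test valid, and its standard error already covers chance imbalance. Only efficiency is in question.
- *The gain may be negligible.* A reader might take the factor (1 + ρ)/2, or a figure such as a third more patients at ρ = 0.5, as a property of this trial. Both need equal log SDs. If nadir counts vary more than baseline counts, the saving shrinks and can be zero. The protocol gives no data to place the trial within the range.
- *The mechanism is unknown.* One might argue that counts depressed by recent chemotherapy recover and produce high ratios. Section 18.1 says nothing about this, so it cannot carry the point.
- *The ratio was chosen for a reason.* Section 18.1 cites evidence that a lower nadir-to-pre-treatment ratio predicted poorer prognosis. Replacing it with nadir alone would demote a declared endpoint. Modelling the log ratio with the baseline as covariate meets this objection, since the group effect is the same.
- *Details are deferred and the work is exploratory.* Both are true, and the later plan could add an adjusted model. But the protocol names the test, and both named options are unadjusted. This is therefore a stated method with a better alternative, not a detail still to come.

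**Conclusion.** The point holds as an efficiency improvement of minor importance. The named comparison is valid but can be less precise than the same blood samples allow. With equal log SDs the variance saving is 10% to 35% for correlations of 0.8 down to 0.3; with a baseline SD of 0.8 of the nadir SD it is 0% to about 22%; it is zero when the true log-scale slope is 1. In power terms, with equal SDs and an assumed log SD of 0.40 and log effect of 0.12, the gap at one-sided 0.05 runs from 16 points (58% to 74%) at a correlation of 0.3 to about 1 point (97% to 98%) at 0.8.

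These figures rest on assumed correlations, SDs and effect, none of which the protocol supplies. The conclusion that adjustment costs nothing beyond one degree of freedom does not depend on their values. The documents do not support reading this as a flaw in the sub-study's validity, in its primary endpoint or in its sample size.

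**What to change.** In section 18.1, and in the sub-study's analysis plan, keep the nadir-to-pre-treatment ratio as the secondary endpoint but replace its unadjusted test. Compare Control with the combined Test Groups by ANCOVA of log(nadir/pre-treatment count) on group, with log pre-treatment count as covariate. Report the adjusted ratio of geometric means with its confidence interval, and tabulate the raw ratio by group for comparison with published work.

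The cost is one sentence in each document and one degree of freedom. No additional samples, patients or assays are needed, and the 240-patient calculation stays as it is. The change should be made before the data are analysed.
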